- a) **Determine the effect of RA, compared with O₂, on maternal and fetal free radical activity.** We will test the *hypothesis* that RA, compared with O₂, for Category II EFM in labor will result in lower maternal and umbilical cord levels of malondialdehyde (MDA) and 4-hydroxynonenal (4-HNE), byproducts of free radical mediated lipid peroxidation and markers of oxidative stress that is associated with neonatal morbidity.
- b) **Investigate the effect of duration of RA or O₂ exposure on maternal free radical accumulation.** We will test the *hypothesis* that the magnitude of maternal free radical activity is directly related to duration of O₂ exposure by serially measuring maternal MDA and 4-HNE levels during labor.
- c) **Investigate the effect of O₂ exposure on placental oxidative stress.** We will test the hypothesis that intrapartum O₂ exposure is associated with increased local oxidative stress in the placenta, as represented by 4-HNE.

Secondary Aim 1 (Exploratory): Determine the impact of RA, compared with maternal O₂ supplementation, on neonatal outcomes in women with Category II EFM in labor. We will evaluate a composite outcome of neonatal morbidity including neonatal death, hypoxic-ischemic encephalopathy, seizures, hypothermia treatment, intubation, mechanical ventilation, and meconium aspiration syndrome in patients randomized to O₂ or RA in labor.

Secondary Aim 2: Determine the relationship between maternal serum and urine markers of oxidative stress during labor

[figure not shown]
The expected outcome of this proposal is high-quality mechanistic evidence for the pathophysiology of in-utero oxygen exposure. If RA is proven to be a more effective and safer option than O₂, it will change the clinical approach to intrauterine resuscitation of millions of women who labor and deliver each year in the U.S.

Background

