Recruitment of Subjects and Randomization: We will use established recruitment techniques employed in recent RCTs performed on L&D at BJH. All women admitted to L&D in spontaneous labor or induction of labor will be screened with the above inclusion and exclusion criteria. Eligible subjects will be approached for written consent to participate on admission to L&D, irrespective of starting cervical dilation. Randomization will be performed only when the patient is in active labor (defined as cervical dilation ≥ 6 cm) and develops Category II EFM necessitating intrauterine resuscitation as determined by the care provider team (**Figure 3**). Using a computer-generated sequence in block sizes of 4, patients will be randomized in a 1:1 ratio to either O₂ or RA.

Figure 3: Enrollment and Randomization of Study Participants

Intervention

1. **O₂ group:** Patients in this group will receive O₂ via nonrebreather face mask at 10L/min (FiO₂ approximately 0.80) [55]
2. **RA group:** Patients in this group will be exposed to RA only and not wear an O₂ mask unless required for maternal hypoxia (FiO₂ approximately 0.21).

Primary Aim 1

Determine the effect of RA, compared with O₂, on maternal and fetal free radical activity.

1. **Hypothesis:** RA, compared with O₂, for Category II EFM in labor will result in lower mean maternal and umbilical cord levels of malondialdehyde, a byproduct of free-radical-mediated lipid peroxidation and a marker of oxidative stress.
2. **Rationale:** MDA and 4-HNE are downstream products of free radical buildup from excess O₂ and are known markers of oxidative stress.. The current use of O₂ for Category II EFM may result in prolonged exposure that generates free radicals and resultant oxidative stress.
To explore the feasibility of MDA analysis in laboring patients and to provide preliminary data for sample size calculation, we performed the Thiobarbituric Acid Reactive Substances (TBARS) assay for MDA quantification in a subset of maternal (n=27) and UA (n=33) samples exposed to O₂ in the above mentioned pilot trial. The mean maternal MDA was 6.5 μ M \pm 1.0 and the mean UA MDA was 8.3 μ M \pm 2.0. Although no conclusions regarding oxidative stress can be made from this data alone, these results demonstrate feasibility of MDA analysis in this setting.

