3. **Data collection:** We will compare maternal and fetal free radical mediated oxidative stress between O₂ and RA groups by measuring MDA and 4-HNE in maternal and umbilical cord blood and placenta samples. Maternal blood will be drawn at time of randomization and within 1 hour of delivery. Per the BJH universal cord gas policy, a segment of the umbilical cord and placenta will be removed after delivery of the infant and trained providers will immediately collect UA and umbilical vein samples for routine cord gas analysis. An additional UA sample will be collected for the purpose of this study. We will employ the services provided by the WUMC Women and Infants Health Specimen Consortium to collect samples in EDTA tubes, centrifuge them, and store the plasma in-80°C freezers.
4. **Outcome:** The *primary outcome* is mean maternal and UA MDA and 4-HNE at time of delivery. We will collaborate with the Washington University at St Louis (WUSTL) Core Laboratory for Clinical Studies (CLCS) to perform the Thiobarbituric Acid Reactive Substances (TBARS) assay for MDA quantification[24, 56] This assay is performed by adding TBA to plasma and performing an ELISA to fluorometrically measuring the resultant MDA-TBA complexes. The CLCS will use the commercially available OxiSelectTM TBARS Assay Kit (Cell Biolabs, Inc) to perform these studies. We will use the OxiselectTM HNE ELISA kit (Cell Biolabs, Inc) to quantify 4-HNE. 4-HNE quantification in placental villi will be determined using immunohistochemistry (IHC). Secondary outcomes include UA cord gases and clinical measures of neonatal morbidity including NICU

admission, neonatal death, intubation, mechanical ventilation, hypoxic ischemic encephalopathy, meconium aspiration syndrome and need for hypothermia therapy.

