5. Data analysis: The primary analysis will be by intention-to-treat. Baseline demographics and secondary outcomes will be compared between RA and O₂ groups using χ^2 , Fisher exact test, Mann-Whitney *U* test, or Student's *t* test as appropriate. The primary outcome, mean maternal and UA MDA, will be compared between groups using the Student's *t* test if normally distributed. If non-normally distributed, the median maternal and UA MDA levels will be compared between groups using the Mann-Whitney *U* test. Linear regression will be used to adjust for relevant covariates. We will perform supplementary analyses including 1) stratified analysis by presence of maternal comorbidities or fetal growth restriction to assess if the effect of O₂ on oxidative stress varies in patients with fetal growth restriction or comorbidities. (2) as-treated analysis to determine whether compliance with the assigned group affects outcomes.
6. Sample size calculation: Based on pilot trial data, the mean UA MDA in 33 patients receiving O₂ for Category II EFM in active labor is $8.3 \pm 2.0 \mu\text{M}$. Assuming a two-sided alpha of 0.05, a total **212 patients (106 O₂ and 106 RA)** will afford 80% power to detect a 10% difference mean UA MDA between O₂ and RA groups, while accommodating for 15% loss due to UA samples. A 10% difference in UA MDA levels may be meaningful as neonatal MDA differences as small as 3-5% are associated with free-radical mediated injuries such as hypoxic ischemic encephalopathy [28, 57] There is limited published data on maternal MDA levels and associated adverse outcomes. However, this sample size will afford >90% power to also detect a 10% difference in maternal MDA between groups. To accommodate a compliance run-in of 6 patients, a total of **218 patients** will be recruited.

Feasibility of the sample size: BJH delivers approximately 4,000 patients per year. Based on results of our pilot trial, 32% of the approached patients meeting eligibility criteria consented to participation in the study. Of the patients enrolled, 40% met criteria for randomization (Category II EFM necessitating intrauterine resuscitation after 6cm dilation). In total, 114 patients were randomized over the study period of 12 months. Therefore, we anticipate successful enrollment of 212 patients within 2.5 years (70-72 patients/year).

Secondary Aim 1:

Investigate the relationship between duration of RA or O₂ exposure and magnitude of oxidative stress

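### Primary Aim 1 defines its primary outcome as four measures in item 4 and two in item 5, and no section names a lead measure or a success rule

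*Combined protocol and SAP*

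**What the plan says.** All references are to the combined protocol and SAP.

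- **Primary Aim 1, item 4 (Outcome):** the primary outcome "is mean maternal and UA MDA and 4-HNE at time of delivery". Two analytes in two compartments make four measures. The secondary outcomes are introduced with "Secondary outcomes include UA cord gases and clinical measures of neonatal morbidity", and 4-HNE is not among those named.
- **Primary Aim 1, item 5 (Data analysis):** "The primary outcome, mean maternal and UA MDA, will be compared between groups" by Student's t test, or by Mann-Whitney if the data are not normal. That is two measures.
- **Specific Aims, Primary Aim a):** the hypothesis is that room air "will result in lower maternal and umbilical cord levels of malondialdehyde (MDA) and 4-hydroxynonenal (4-HNE". **Primary Aim 1, item 1 (Hypothesis):** room air "will result in lower mean maternal and umbilical cord levels of malondialdehyde", with no mention of 4-HNE. These are hypotheses rather than outcome definitions, but they differ in the same way.
- **Primary Aim 1, item 6 (Sample size calculation):** "Assuming a two-sided alpha of 0.05", 212 patients "will afford 80% power to detect a 10% difference mean UA MDA between" the arms, "while accommodating for 15% loss due to UA samples". The item adds that power for a 10% difference in maternal MDA exceeds 90%. It says nothing about 4-HNE.
- **Safety Monitoring** and **Data and Safety Monitoring Plan (Criteria for stopping the study):** a Haybittle-Peto threshold of p<0.001 applies at 50% recruitment to the primary outcome, with no measure named.
- **Status of the other components:** Specific Aims places the duration analysis (b) and placental 4-HNE (c) under the Primary Aim. The body of the protocol heads the duration analysis Secondary Aim 1 and gives it a primary outcome of its own. In Specific Aims, the label Secondary Aim 1 belongs to neonatal outcomes.

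**The concern.** Items 4 and 5 are adjacent, both are current text, and both use the label primary outcome for different sets of measures. A reader cannot tell whether 4-HNE counts towards the trial's main conclusion. If it does, half of that outcome has no between-group test assigned to it as primary, and no mean, SD or power.

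Even the two-measure version lacks a decision rule. Nothing says whether a difference in UA MDA alone, in maternal MDA alone, or in both is needed to confirm the hypothesis. Suppose that neither MDA comparison reaches 0.05 but a 4-HNE comparison does. Under an any-one rule, item 4 would make the trial positive and item 5 would make it negative. Under an all-must-succeed rule, both would make it negative. The plan does not say which rule applies, and that choice should not remain open once results are known.

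The interim rule has the same gap. The candidate measures differ widely in their chance of crossing p<0.001, so the unnamed measure could affect whether the trial continues.

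**Working it through.** **Inputs from the plan.** UA MDA has mean 8.3 and SD 2.0 µM, so a 10% difference is 0.83 µM. Maternal MDA has mean 6.5 and SD 1.0 µM, so a 10% difference is 0.65 µM. Alpha is two-sided 0.05, allocation is 1:1 with 106 per arm, and 15% of UA samples are expected to be lost. No mean, SD or effect size is given for 4-HNE.

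**Assumptions.** The plan gives no correlations between measures; those used below are assumed and equal across measures. Maternal samples are taken as complete unless stated.

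**1. The plan's own N.** n per arm = 2 × (1.960 + 0.842)² × (2.0/0.83)² ≈ 91.1, rounded up to 92. Then 92 × 1.15 = 105.8, or 106 per arm and 212 in total, which is the plan's figure. It comes from one UA MDA test at an unsplit 0.05.

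**2. Power at that N.** Evaluable UA samples: 106 × 0.85 ≈ 90 per arm.

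| Measure | n per arm | Power, two-sided 0.05 |
|---|---|---|
| UA MDA | 90 | 79.1% (t), 79.5% (normal) |
| Maternal MDA | 106 | 99.7% |
| Maternal MDA, if 15% were also lost | 90 | 99.2% |
| 4-HNE, any compartment | – | cannot be computed |

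Both MDA measures together: 0.791 × 0.997 ≈ 0.79 under independence.

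**3. Type I error by success rule.**

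| Rule | Two measures | Four measures |
|---|---|---|
| Any one at 0.05, independent | 1 − 0.95² = 9.75% | 1 − 0.95⁴ = 18.5% |
| Any one at 0.05, correlation 0.8 | 7.8% | 11.4% |
| Any one at 0.05, correlation 0.9 | 7.0% | 9.4% |
| All must succeed | ≤5% | ≤5% |

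**4. How often the two definitions would disagree.** Under no true effect and an any-one rule, the four-measure version is positive while the MDA-only version is negative with probability equal to the difference between the columns:

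- independent: 18.5 − 9.75 ≈ 8.8%
- correlation 0.8: 11.4 − 7.8 = 3.6%
- correlation 0.9: 9.4 − 7.0 = 2.4%

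**5. Interim look at p<0.001.** The false-positive consequence is small: 1 − 0.999² = 0.2% for two independent tests and 1 − 0.999⁴ = 0.4% for four. At the planned effects, the chance of crossing is about 8% for UA MDA (45 per arm) and about 49% for maternal MDA (53 per arm).

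**The case against.** The strongest reply is that UA MDA is already the primary measure in all but name. Item 6 ties alpha, power, sample loss and N to it and treats maternal MDA as an addition. This stands as a description of how the trial was sized. It does not settle the outcome definition, because item 5 expressly calls maternal and UA MDA together the primary outcome, and nothing says that item 6 overrides items 4 or 5.

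A second reply is that the wording joins the measures with *and*, which suggests that all must succeed, in which case the error cannot exceed 5%. That reading is available, but the plan never states it as a rule.

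A third is that the test for 4-HNE is obvious. Item 3 plans to compare the groups on both analytes, and item 5 lists the t and Mann-Whitney tests for secondary outcomes too. This largely stands: the choice of test is not in real doubt, only the status of the result. The secondary list is also worded as non-exhaustive, so the absence of 4-HNE from it proves little.

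Finally, the interim threshold only guides further conduct and carries little false-positive risk. That is correct; the reason to name its measure is clarity of the decision.

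Two stronger readings may tempt a reader, and the documents support neither. One is that the trial runs a type I error of up to 18.5%. That needs an any-one rule, which no section states, and independence between measures. The other is that the sample size is wrong. It reproduces for a single UA MDA test.

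**Conclusion.** The concern holds as a direct contradiction between items 4 and 5 of Primary Aim 1, together with a missing success rule. The differing hypotheses echo the contradiction but do not by themselves define a primary outcome.

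The overall error rate is undefined: at most 5% if all measures must succeed, and from about 7% to 18.5% under an any-one rule, depending on the number of measures and on a correlation assumed between 0.9 and 0. Joint power that includes 4-HNE cannot be established from the documents.

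The duration and placental analyses are not cleanly separate from this problem, because Specific Aims lists both under the Primary Aim while the body treats duration as secondary. The matter should be settled before results are known, since it determines what counts as a positive trial.

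**What to change.** Before any unblinded outcome data are seen:

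1. In Primary Aim 1, items 4 and 5, name UA MDA at delivery as the single primary outcome, tested at two-sided 0.05. Name the same measure in the interim rule under Safety Monitoring and under Criteria for stopping the study.
2. State that maternal MDA at delivery is tested next, at two-sided 0.05, only if UA MDA succeeds.
3. List maternal, UA and placental 4-HNE as secondary outcomes, with the t or Mann-Whitney comparison written into item 5.
4. Align the hypotheses in Specific Aims, Primary Aim a), and in Primary Aim 1, item 1, with this order.
5. Reconcile Specific Aims with the body on the status of the duration analysis and of placental 4-HNE. Call the measure in item 3 of the duration section the main outcome of that secondary aim, and resolve the double use of the label Secondary Aim 1.

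The cost is wording only. N stays at 212, no assays are added, and power for the primary test is about 79% at 90 evaluable UA samples per arm. The price of the fixed order is that maternal MDA and 4-HNE cannot carry a primary claim if UA MDA misses significance, which happens in 1 − 0.791 ≈ 21% of trials at the design effect.

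The documents do not show whether the 50% interim look has taken place. If it has, people who have not seen its results should fix and date the definition.

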We propose a randomized controlled trial to investigate maternal and fetal free radical activity in laboring patients with Category II EFM exposed to O₂ or RA. A randomized controlled trial, the ‘gold-standard’ of study design, was chosen to produce high quality evidence on the safety of O₂ administration for Category II EFM. Our central hypothesis is that prolonged intrauterine exposure to O₂ during labor, compared with RA, generates free radicals that have downstream biochemical and clinical consequences to the neonate. This trial will be conducted on Labor and Delivery (L&D) at Washington University Medical Center (WUMC). Patients ≥37 weeks gestational age in active labor (≥6 centimeters cervical dilation) with Category II EFM necessitating intrauterine resuscitation (as determined by the care provider team) will be randomized to RA or maternal O₂ administration of 10L/min via nonrebreather face mask until delivery. All other resuscitation techniques (maternal repositioning, intravenous fluid bolus, etc) will be left to the discretion of the care provider team. EFM strips will be read and interpreted by the study nurse coordinator. Maternal blood, collected at randomization and within 1 hour post-delivery, placenta and umbilical artery blood collected at the time of delivery will be used to run MDA analyses. Maternal urine will be collection on enrollment (prior to rupture of membranes or cervical dilation <6cm), at time of randomization, and within 1 hour of delivery. At any of these time points, if patient has a foley catheter, the urine may be collected from the catheter. If patient does not have a catheter, either a straight catheterization can be performed or a clean catch sample can be obtained. The same commercially available assays used to quantify MDA and 4-HNE in our blood samples will be used for the urine samples.

Study staff will extract data from medical records including maternal demographics, antepartum history, intrapartum management, delivery outcomes, and neonatal outcomes. The patient’s primary nurse will perform real-time documentation of O₂ or RA initiation, any disruption in intervention, administration of amnioinfusion and additional resuscitation techniques performed (number of times patient is repositioned, total intravenous fluids, discontinuation of oxytocin).

Conduct of Trial

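### Maternal MDA: the named between-arm test leaves out the value drawn at randomization, and the planned regression neither names it nor is given a status; the cost is precision only

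*Combined protocol and SAP*

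**What the plan says.** Primary Aim 1, item 4 Outcome, states that the primary outcome "is mean maternal and UA MDA and 4-HNE at time of delivery". Item 5 Data analysis then sets the comparison: "The primary outcome, mean maternal and UA MDA, will be compared between groups using the Student's" t test, with Mann-Whitney U if the values are not normally distributed. One further sentence provides for linear regression with covariates judged relevant. It does not list them, does not mention the randomization value, and does not say whether the regression is the primary or a supporting analysis.

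The randomization sample is planned throughout. Item 3 Data collection says "Maternal blood will be drawn at time of randomization and within 1 hour of delivery", in the paragraph that introduces the between-arm comparison. The Overview under Research Design and Methods says "Maternal blood, collected at randomization and within 1 hour post-delivery, placenta and umbilical artery blood collected at the time of delivery will be used" for the MDA analyses. Secondary Aim 1, item 2, and Table 2 repeat the two maternal draws. Primary Aim b) gives the serial values a second purpose, the duration question, to be studied "by serially measuring maternal MDA and 4-HNE levels during labor".

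The cord has no earlier sample. Secondary Aim 1, item 2, says that repeated cord sampling is not feasible.

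**The concern.** A pre-exposure measurement of the same marker is often the most useful covariate for a continuous outcome. Here it is drawn and assayed in every randomized woman, yet the test that decides the maternal part of the primary outcome does not use it. If randomization and delivery values are correlated, the maternal effect will be reported with a wider interval than the planned samples allow.

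The wording also leaves two choices open: whether the randomization value counts as a relevant covariate, and which maternal result is primary if the regression and the t test differ. Both are best settled before anyone sees data by arm. Maternal 4-HNE is in the primary outcome as well, and the same model would serve it.

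**Working it through.** **Inputs from the documents**
- Maternal MDA: "The mean maternal MDA was 6.5" μM with SD 1.0 μM, from 27 O₂-exposed pilot samples (Primary Aim 1, item 2). A 10% difference is 0.65 μM.
- UA MDA: mean 8.3, SD 2.0 μM. A 10% difference is 0.83 μM.
- 106 women per arm, two-sided alpha 0.05 (item 6).

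**Assumptions**
- SD of 1.0 μM at both times and in both arms.
- 106 complete mothers per arm. As a variant, 90 per arm: 106 × 0.85 = 90.1, applying to mothers the 15% loss that item 6 gives for UA samples only.
- r = 0.2, 0.3, 0.5 or 0.7. The documents give no value.

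**Step 1: the plan's own figures**
- UA sample size: 2 × [2.0 × (1.960 + 0.842) / 0.83]² = 91.1, so 92 per arm. 92 × 1.15 = 105.8, so 106 per arm and 212 in total, as stated. The total is driven by UA MDA, which has no baseline.
- Maternal power: SE = 1.0 × √(2/106) = 0.1374 μM, and 0.65 / 0.1374 = 4.73. Power from the noncentral t distribution is 99.7% (99.1% with 90 per arm). This agrees with the stated figure of more than 90%.

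**Step 2: gain from adjustment**

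Adjusted SE = 0.1374 × √(1 − r²). The half-width is this SE times the t quantile, 1.971 on 210 df unadjusted and 209 df adjusted.

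| r | Variance reduction (r²) | Half-width, 106 per arm (μM) | Half-width, 90 per arm (μM) |
|---|---|---|---|
| unadjusted | none | 0.271 | 0.294 |
| 0.2 | 4% | 0.265 | 0.288 |
| 0.3 | 9% | 0.258 | 0.281 |
| 0.5 | 25% | 0.235 | 0.255 |
| 0.7 | 49% | 0.193 | 0.210 |

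The documents give no mean or SD for 4-HNE, so only the variance column carries over to it.

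**Step 3: validity of the unadjusted test**

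In a simulation of 20,000 trials per setting (106 per arm; r = 0.3, 0.5, 0.7), both methods recovered the true difference to within 0.002 μM. Type I error was 4.8% to 5.2% for both. Leaving out the baseline widens the interval and does nothing else.

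**Step 4: interim look**

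Safety Monitoring and the Data and Safety Monitoring Plan apply p<0.001 to the primary outcome at 50% recruitment. With 53 per arm and a true 0.65 μM, the chance of meeting that rule on maternal MDA is 49% unadjusted. Adjusted, it is 51%, 55%, 68% or 90% at the four values of r. Changing the interim test would therefore change the stopping behaviour.

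**Step 5: late baseline draws**

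If a share of O₂-arm baselines were drawn after exposure began and already carried part of the effect, the adjusted estimate would shrink by r × share × fraction carried. With an assumed 10% share at full effect, the shrinkage is 2%, 3%, 5% or 7% at the four values of r.

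**The case against.** The strongest reply is that nothing is broken. The test is valid, maternal power for the planned difference is close to 100%, and the sample size rests on an outcome with no baseline. The gain depends on an unknown r. A low r is plausible, because exposure lasts from under 30 to over 90 minutes within a group. All of this stands, and it is why the point is low severity. It does not remove the point, because the 99.7% applies only to a 10% difference, and item 6 itself says that published maternal data are limited. For an illustrative 5% difference (0.325 μM, a figure chosen here), power with 106 per arm is 65% unadjusted and 67%, 69%, 78% or 91% adjusted at r = 0.2, 0.3, 0.5 or 0.7.

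A second reply is that the planned regression may already cover this. The randomization value fits its wording and is not excluded. That is fair. What remains is that the value is not named and the model has no stated status.

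A third reply is that a draw at randomization naturally precedes exposure. That may be so, but the extracted text does not state the order, and Figure 3, on enrollment and randomization, is not shown. Randomization happens once a patient "develops Category II EFM necessitating intrauterine resuscitation as determined by the care provider team", so time may be short. A reader might infer that the baseline is contaminated by exposure. The documents do not show that; the order simply needs to be confirmed.

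**Conclusion.** The point holds as a low-severity matter of precision, for maternal markers only. The named tests do not use the randomization value, and the regression neither names it nor is called primary or supportive. The achievable narrowing of the maternal 95% CI runs from about 2% (0.271 to 0.265 μM at r = 0.2) to about 29% (0.271 to 0.193 μM at r = 0.7). This rests on an assumed r and on one SD from 27 O₂-exposed pilot samples.

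Three stronger readings are not supported:
- A reader might infer that the maternal comparison is biased or underpowered. Randomization makes the unadjusted comparison valid, and its power for the stated target exceeds 99%.
- A reader might infer that the randomization sample is collected to no purpose. The Overview assigns it to MDA analysis, and Primary Aim b) plans serial values.
- A reader might infer that adjustment would allow a smaller trial. The total of 212 comes from UA MDA, which adjustment does not touch.

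**What to change.** In Primary Aim 1, item 5, before any by-arm look including the 50% interim:
- Name as the primary maternal analysis a linear model of the delivery value on arm and the randomization value of the same marker, for MDA and likewise for 4-HNE. Log-transform both values if they are skewed.
- Keep the t or Mann-Whitney test as the sensitivity analysis.
- State that the baseline is the sample drawn at randomization before the assigned exposure starts, and record the draw time. If the team cannot confirm that order, keep the unadjusted test primary.

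If by-arm data have already been seen, keep the unadjusted test primary and list the adjusted model as a named secondary analysis.

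In Safety Monitoring and in the Data and Safety Monitoring Plan, say that the p<0.001 rule uses the unadjusted test already named in item 5, so that the stopping behaviour is unchanged.

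The cost is a few sentences and one recorded time. No new samples are needed, and the Overview already says that the patient's "primary nurse will perform real-time documentation of O₂ or RA initiation". The downsides are one degree of freedom, little gain if r is low, and a slightly shrunken estimate if some baseline draws follow the start of exposure.
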